The total duration of participation is approximately 26 weeks. Subjects will be required to visit the study center up to 12 times inclusive of 1 additional follow-up safety visit. During the study, subjects will participate in safety and efficacy assessments as well as pharmacokinetic blood sampling; DcR3 genotyping (CD only); measurement of LIGHT (Lymphotoxin-like, exhibits Inducible expression, and competes with Herpes Virus Glycoprotein D for Herpesvirus Entry Mediator, a receptor expressed by T lymphocytes), selected cytokines; ribonucleic acid (RNA) sequencing; flow cytometry of peripheral blood leukocytes; and quality of life assessment. Subjects currently receiving treatment with biologic therapies will be required to participate in a wash-out period, during which biologic treatment will be discontinued.

Number of patients (planned):

Approximately 14 total subjects will be enrolled as follows:

- 4 subjects with CD in the 1 mg/kg cohort
- 4 subjects with CD in the 3 mg/kg cohort
- 6 subjects with UC in the 3 mg/kg cohort

Diagnosis and main criteria for inclusion:

Inclusion criteria - Crohn's Disease:

1. Subject is able to speak English fluently and has provided written informed consent for this study.
2. Subject is male or female, ≥ 18 to ≤ 75 years of age.
3. Subject has a documented diagnosis of CD via endoscopy/colonoscopy and histological confirmation. Prior documentation of histological confirmation is acceptable.
4. Subject has moderate to severe, active CD as evidenced by Simple Endoscopy Score for Crohn's Disease (SES-CD) score of ≥ 7 .
5. Subject has failed treatment with an approved therapeutic dose of an anti-TNF α monoclonal antibody treatment with either no initial response (primary non-responder) or an initial response to induction with subsequent lost response (secondary non-responder) as defined in the protocol.
6. Subject can be receiving concurrent treatment with an oral corticosteroid, and/or azathioprine or 6-mercaptopurine (6-MP) or methotrexate (MTX) as defined in the protocol.
- 7.
8. Subject agrees to be genotyped at the DcR3 locus.

Exclusion criteria - Crohn's Disease:

1. Subject has a diagnosis of ulcerative colitis (UC) or indeterminate colitis.
2. Subject is unable to tolerate or unwilling to undergo study procedures including endoscopy and biopsy during the study.
3. Subject with signs or symptoms of bowel obstruction with small bowel imaging supporting obstruction.

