8. INVESTIGATIONAL PLAN

8.1. Overall Study Design

This is a Phase 1b, multi-center, open-label, dose-escalation, signal-finding study to evaluate the safety, tolerability, PK and short-term efficacy of MDGN-002 in adults with moderate to severe, active CD or UC who have previously failed anti-TNF α treatment.

Four subjects with Crohn's disease who satisfy all eligibility criteria will be enrolled in each of 2 dose cohorts. The first cohort will receive MDGN-002 1.0 mg/kg SQ every 14 (q14) days. Dose escalation will proceed after all subjects in the first cohort have been enrolled and reached Visit 4 (Day 14 \pm 3 days), the safety data from those subjects has been reviewed by the Data Monitoring Committee, and a decision has been made to progress to the second cohort (see [Section 8.4](#)). The estimated dose escalation for the second cohort is 3.0 mg/kg SQ q14 days, if permitted by safety data review. After dose escalation has taken place 6 additional patients with UC will also be enrolled in the 3 mg/kg cohort.

Each subject's participation will include a screening period, which if required includes a wash-out period for subjects who have received biologic treatment within 12 weeks of the Screening Visit. With the exception of subjects requiring wash-out of the biologic certolizumab pegol (Cimzia), only those subjects without detectable biologic levels after 8 weeks of wash-out will be allowed to enter the study after confirmation of undetectable levels; all other subjects (including those receiving certolizumab pegol [Cimzia]) will be required to complete a full 12-week wash-out period. The wash-out period includes the time period from the last dose received prior to the Screening Visit. Subjects not requiring a biologic wash-out period will be allowed to enter the study after review and confirmation of eligibility at screening. Screening is followed by an 8-week, open-label treatment period, and a safety follow-up visit approximately 4 weeks after the last dose. The maximum study duration is 26 weeks.

Study visits will occur at screening and on Days 0, 7, 14, 21, 28, 35, 42, 49 and 56. The safety follow-up visit will occur on Day 84. The Schedule of Assessments is shown in [Table 1](#).

Table 1 Schedule of Assessments

Assessment or Procedure	Screening Period				Open-Label Treatment Period										Safety Follow-up	

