	Visit 1	Initial Phone Contact ^a	Visit for Testing Previous Biologics (if required)	Wash-out Phone Contact ^b	Visit 2 ^c		Visit 3 Day 7	Visit 4 Day 14	Visit 5 Day 21	Visit 6 Day 28	Visit 7 Day 35	Visit 8 Day 42	Visit 9 Day 49	Visit 10 / ET Visit Day 56		
					Pre-dose Day 0	Dosing and Post-dose Day 0										
Informed consent	X															
Inclusion/exclusion criteria review	X	X			X											
Testing for Previous Biologics			X ^d													
Genotyping for DcR3 genes (CD only)	X															
Demographics / medical history ^d	X															
Physical examination, incl. weight ^e	X				X			X		X		X		X		
Vital signs (BP, pulse, RR, T) ^f	X				X	X		X		X		X		X		
TB testing ^g	X															
12-lead ECG	X									X				X		
Clinical laboratory assessments ^h	X				X			X		X		X		X		

Assessment or Procedure	Screening Period				Open-Label Treatment Period										Safety Follow-up	
	Visit 1	Initial Phone Contact ^a	Visit for Testing Previous Biologics (if required)	Wash-out Phone Contact ^b	Visit 2 ^c		Visit 3 Day 7	Visit 4 Day 14	Visit 5 Day 21	Visit 6 Day 28	Visit 7 Day 35	Visit 8 Day 42	Visit 9 Day 49	Visit 10 / ET Visit Day 56		
					Pre-dose Day 0	Dosing and Post-dose Day 0										
Adverse event monitoring ^o	X	X	X	X	X	X	X	X	X	X	X	X	X	X	X	
Concomitant medications	X	X	X	X	X	X	X	X	X	X	X	X	X	X	X	
Provide/re- confirm access to subject diary	X				X		X	X	X	X	X	X	X	X		
Subject diary reviewed for completeness					X		X	X	X	X	X	X	X	X		
Assess individual subject stopping criteria						X	X	X	X	X	X	X	X	X		
MDGN-002 administration (on-site) ^p						X		X		X		X				

^a Telephone visit is conducted for confirmation of eligibility. If the subject is not currently receiving biologic treatment, they will begin completing the subject diary and have visit 2 scheduled >7 days from the diary being initiated. The diary should be completed up to the time of the visit.

^b Telephone visit is conducted for confirmation whether additional wash-out time is required following receipt and review of the laboratory results. If the concentration level is not detectable, the subject will have their visit scheduled >7 days from the time the subject started completing the diary. If the concentration level is detectable, the subject will complete the full 12 week wash-out. The diary should be completed up to the time of the visit.

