^q Subjects requiring wash-out will have a blood test performed at 8 weeks after the start of the wash-out period to confirm the previous biologic therapy is undetectable. If there is no previous biologic therapy detected, subjects will be able to continue onto Visit 2 and will not be required to complete the full 12-week wash-out. If there are detectable levels of the previous biologic therapy, then subjects will complete the full 12-week wash-out before proceeding to Visit 2. For subjects receiving certolizumab pegol (Cimzia) a 12-week wash-out is required.

^r The Modified Mayo Score includes stool frequency, rectal bleeding, and the appearance of mucosa upon endoscopy. This score will be calculated at Visit 1 and Visit 10 using the endoscopy score from the central reader, self reported data on stool frequency and rectal bleeding from the period prior to the subject being screened for Visit 1 and data from the patient diary for Visit 10.

BP=blood pressure; CBC=complete blood count; CDAI=Crohn's Disease Activity Index; CRP=C-reactive protein; DcR3=decoy receptor 3; GGT=gamma-glutamyl transferase; ECG=electrocardiogram; ET=early termination; hCG=human chorionic gonadotropin; LIGHT=Lymphotoxin-like, exhibits Inducible expression, and competes with Herpes Virus Glycoprotein D for Herpesvirus Entry Mediator, a receptor expressed by T lymphocytes; PK=pharmacokinetic; PPD = purified protein derivative; RR=respiration rate; T=temperature; TB=tuberculosis; TNF α =tumor necrosis factor alpha.

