Subjects who are currently taking a biologic treatment or who have received biologic treatment within 12 weeks of the Screening Visit but who are otherwise eligible for study participation based on review of all screening evaluations and results will begin a wash-out period for these medications. Washout is the period between when the subject received their last dose of biologic and when they are eligible to proceed to Visit 2. With the exception of subjects requiring wash-out of the biologic certolizumab pegol (Cimzia), a blood test will be administered to subjects undergoing wash-out 8 weeks after their last dose of biologic treatment to ensure that serum levels of any previous biologic treatments are below the level of detection. If it is confirmed that the levels of previous biologic treatment are undetectable, then the subject will proceed to Visit 2. If the test results indicate that the previous biologic treatment is detectable, the subject will be required to complete a full 12-week wash-out period before proceeding to Visit 2. For subjects receiving the biologic certolizumab pegol (Cimzia) a 12-week wash-out is required.

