12.1.2. Eligibility Check/Wash-Out Period

Each subject will receive a telephone call to confirm continued subject eligibility. For subjects not requiring a wash-out period the subject may return for Visit 2 once the diary has been completed for a minimum of 7 days immediately prior to dosing. Visit 2 should be completed no sooner than Day 8 from the time diary completion was initiated. Any changes in concomitant medication use and any newly occurring AEs since the last evaluation will be recorded.

With the exception of subjects who most recently received the biologic certolizumab pegol (Cimzia), subjects requiring a wash-out will have a blood test administered 8 weeks after their last dose of biologic treatment to ensure that serum levels of any previous biologic treatments are below the level of detection. If it is confirmed that the levels of previous biologic treatment are undetectable and the subject has completed the diary for a minimum of 7 days immediately prior to dosing, the subject may return for Visit 2. Visit 2 should be completed no sooner than Day 8 from the time diary completion was initiated. If the test results indicate that the previous biologic treatment is detectable, the subject will be required to complete a full 12-week wash-out period. For subjects receiving the biologic certolizumab pegol (Cimzia) a 12-week wash-out is required. The diary should be completed up to the time of the visit. Any changes in concomitant medication use and any newly occurring AEs since the last evaluation will be recorded.

If the subject is not eligible, the subject should have any changes in concomitant medication use and any newly occurring AEs since the last evaluation recorded and should be removed from screening.

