2. STUDY DESIGN AND PROCEDURES

This is a Phase 1b, open-label, dose-escalation, signal-finding, multi-center study to evaluate the safety, tolerability, pharmacokinetics, and short-term efficacy of MDGN-002 in adults with moderate to severe, active CD or UC who have previously failed anti-TNFα treatment. The study is a pilot study using a dose-escalation design to characterize the safety and tolerability of 2 different doses of MDGN-002 (1.0 mg/kg and 3.0 mg/kg) in the CD population, and 3.0 mg/kg in the UC population. All subjects will receive a total of 4 doses of MDGN-002 by SQ injection at 14-day intervals. The study will consist of a screening period, an open-label treatment period and a safety follow-up visit.

In this document, MDGN-002 will be referred to as "study drug" regardless of dosage, and "cohort" will refer to 1.0 mg/kg (Cohort 1) or 3.0 mg/kg (Cohort 2) as described above.

The following study visits will be performed:

- Visit 1 (Screening). This period may be up to 14 weeks, inclusive of a washout period for subjects who have received a biologic treatment within 12 weeks of Visit 1. The amount of time required is determined based on the subject's last dose of the medication and may be up to 12 weeks.
- Visit 2 (Pre-/Post-Dose Day 0);
- Visit 3 (Day 7);
- Visit 4 (Pre-/Post-Dose Day 14);
- Visit 5 (Day 21);
- Visit 6 (Pre-/Post-Dose Day 28);
- Visit 7 (Day 35);
- Visit 8 (Pre-/Post-Dose Day 42);
- Visit 9 (Day 49);
- Visit 10 (Day 56/Early Termination (ET));
- Visit 11 (Day 84 or 28 days after ET).

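### Table 1 footnote a releases any subject not currently on a biologic to Visit 2, with none of the 12-week look-back that Protocol 8.1, 8.2.1 and SAP 2 require

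*Protocol*

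**What the plan says.** Protocol Table 1, footnote a, covers the initial phone contact at which eligibility is confirmed. It reads: "If the subject is not currently receiving biologic treatment, they will begin completing the subject diary and have visit 2 scheduled", with Visit 2 more than 7 days after the diary starts. Current treatment is its only condition.

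Three other places set the wash-out trigger by date:

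- Protocol 8.1: screening includes, if required, "a wash-out period for subjects who have received biologic treatment within 12 weeks of the Screening Visit". Certolizumab pegol apart, early entry is restricted: "only those subjects without detectable biologic levels after 8 weeks of wash-out will be allowed to enter the study". Everyone else in wash-out completes 12 weeks.
- Protocol 8.2.1: wash-out applies to "Subjects who are currently taking a biologic treatment or who have received biologic treatment within 12 weeks of the Screening Visit", if otherwise eligible.
- SAP 2: the screening period is "inclusive of a washout period for subjects who have received a biologic treatment within 12 weeks of Visit 1".

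Two places use the trigger without defining it. Protocol 12.1.2 says "For subjects not requiring a wash-out period the subject may return for Visit 2" once the diary has run for 7 days. Table 1 footnote q says "Subjects requiring wash-out will have a blood test performed at 8 weeks after the start of the wash-out period".

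The synopsis mentions only current users: "Subjects currently receiving treatment with biologic therapies will be required to participate in a wash-out period".

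Protocol 12.3.1.5.6 gives the purpose of the wash-out: to keep earlier biologics from confounding the effects of MDGN-002.

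**The concern.** Section 8.2.1 lists current users and recent users as two separate groups, so being a current user does not already include having stopped recently. Footnote a tests only the first. Followed literally, it sends a subject who stopped a biologic a few weeks before screening straight to the diary and Visit 2, with neither the 8-week level test nor the 12 weeks.

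Prior biologic exposure is universal here, because every subject must have failed an anti-TNF antibody. The groups are also very small: one misrouted subject is 1/4 = 25% of a CD cohort or 1/6 = 16.7% of the UC group. Safety data from the first four CD subjects inform the escalation decision. The SAP plans no subgroup or sensitivity analysis that would set such a subject apart.

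**Working it through.** **Which rule is the protocol's rule.** Sections 8.1 and 8.2.1 define who needs wash-out, and SAP 2 agrees. Section 12.1.2 and footnote q rely on that definition. The synopsis is incomplete about recent stoppers but does not say they are exempt. Only footnote a gives a release condition that differs.

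**Whether a later check catches a misrouted subject.** The pre-dose list at Visit 2 (Protocol 12.1.3.1.1) has 13 steps. Step 1 reviews the inclusion and exclusion criteria, and no step asks about wash-out. The limits on timing of earlier treatment are:

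- natalizumab, 5 years (exclusion 14 in both 9.2 and 9.4);
- investigational biologics, 8 weeks (9.4, exclusion 17; extended to all subjects by 10.2.2);
- tofacitinib, 2 weeks (9.4, exclusion 18).

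No numbered criterion uses the last-dose date of infliximab, adalimumab, certolizumab pegol, golimumab, vedolizumab or ustekinumab. Section 10.2.2 bars biologics during the study. It also has a 2-week phrase whose reach over the listed drugs is unclear, but no 12-week look-back.

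**Size of the gap.** Let d be the days from last dose to Visit 1, and s the days from Visit 1 to Visit 2. Day 0 then falls d + s days after the last dose. The protocol's two marks are 8 × 7 = 56 days and 12 × 7 = 84 days. Day 0 precedes the 8-week test point if d < 56 − s, and precedes 12 weeks if d < 84 − s.

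| s (days) | Basis | 56 − s | 84 − s |
|---|---|---|---|
| 14 | Protocol 12.2, about 2 weeks | 42 | 70 |
| 21 | assumption | 35 | 63 |
| 28 | assumption | 28 | 56 |
| 8 | assumption: diary starts at Visit 1 | 48 | 76 |

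The last row is an outer limit only. Footnote a starts the diary at the telephone call, so s is the call day plus at least 8; s = 14 means a call by day 14 − 8 = 6.

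With s = 14:

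- d below 42: Day 0 comes before the 8-week test point.
- d from 42 to 69: Day 0 falls at 56 to 83 days. The required level test is skipped or, for certolizumab pegol, 12 weeks have not passed.
- d of 70 or more: 70 + 14 = 84, so 12 weeks have passed in any case.

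Example: for d = 28, Day 0 is at 28 + 14 = 42 days. That is 56 − 42 = 14 days before the test point and 84 − 42 = 42 days short of 12 weeks.

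**The case against.** The strongest reply is that this is a slip in one footnote of a protocol that is otherwise clear. A reader might infer that footnote a controls who is released at the eligibility call, so that the protocol as written admits recent stoppers without wash-out. The documents do not support that. Section 12.1.2 is the procedure section for the same call, and it releases only subjects who do not require wash-out. Section 8.2.2 places Visit 2 after the wash-out period where one applies. Sections 8.2.1 and 12.3.1.5.6 say that wash-out must be complete before Visit 2. Table 1 itself has columns for the level-test visit and the wash-out call. This stands, and it confines the risk to a site that works from Table 1 or the synopsis without the body text.

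A reader might also infer that every last dose inside the calculated window would be released. That goes too far as well. The documents do not define current receipt, and a patient between scheduled doses may well count as still on treatment. The 28-day example equals one interval of the 4-weekly golimumab regimen in Appendix 18.2. For d from 42 to 69 days, a subject on another agent with an undetectable level could properly be dosed. What is lost there is the test, not necessarily the interval.

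Finally, a new criterion would repeat a rule that is already mandatory, and the investigator-judgement criteria (9.2, items 23 and 24; 9.4, items 25 and 26) could stop a case. Both points are fair. But those criteria are not specific to wash-out, and the Visit 2 review works from the numbered lists, so one explicit line is a useful backstop.

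**Conclusion.** The conflict is real but narrow. Footnote a is the only release condition that departs from the 12-week rule; the rest of the protocol states or follows that rule. It matters for a site that relies on Table 1 or the synopsis, and for a recent stopper whom that site no longer counts as receiving a biologic. At the stated screening length of about 14 days, the two rules part for last doses up to 69 days before Visit 1. Longer screening narrows that range, but at the lengths examined does not close it.

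The documents do not show how many subjects fall in the range, or that any was dosed early. No planned statistic changes. The case for acting is that the wash-out exists to prevent confounding, the groups are of four to six subjects, and no numbered criterion at Visit 2 specifically covers the omission.

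**What to change.** In footnote a, release a subject to the diary and Visit 2 only if neither limb of the 8.2.1 wording applies: "Subjects who are currently taking a biologic treatment or who have received biologic treatment within 12 weeks of the Screening Visit". Use the same two limbs in the synopsis sentence that says who must undergo wash-out.

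As a backstop, add one line to both the CD and UC criteria, checked at Visit 2: wash-out is complete, meaning an undetectable level at 8 weeks or more after the last dose, or 12 weeks since the last dose (always 12 weeks for certolizumab pegol).

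The cost is a small wording amendment, which under Protocol 14.6 needs the sponsor's written approval, investigator signature and IRB approval. No new data, test or visit is needed: dates of prior therapies are already recorded at screening (8.2.1), and the level test is already planned.

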8.2. Study Periods

The study includes a screening period, an open-label treatment period, and a safety follow-up visit. Each cohort will complete the study periods described below. Following a review of the safety data, a decision will be made whether or not to escalate to the 3 mg/kg as described in [Section 8.4](#).

8.2.1. Screening Period

During the screening period, all subjects will be evaluated for their eligibility to participate in the study. At Visit 1, subjects will sign the informed consent form before any study-related procedures or evaluations are conducted.

Demographic information will be obtained along with medical history, including CD/UC diagnostic information, CD/UC-related procedures/surgeries and medication use history. Any existing conditions reported at the screening visit will be recorded in the electronic case report form (eCRF); current medications will also be recorded on the eCRF. Prior CD/UC therapies (lifetime recall) will be recorded in the eCRF with dates reflecting prior use. All safety assessments will be conducted, including physical examinations (with weight measurements), vital signs (blood pressure, pulse, respiration rate and temperature), 12-lead ECGs, clinical laboratory tests, stool sample and urinalysis. A urine drug screening test (as warranted) and tuberculosis (TB) testing defined as either a purified protein derivative (PPD) skin reaction test or QuantiFERON-TB Gold (QFT) blood test, and as required by protocol, chest x-ray, will be administered to all subjects. A serum β -human chorionic gonadotropin (β -hCG) test will be administered to females of childbearing potential. The CDAI and the Inflammatory Bowel Disease Questionnaire (IBD-Q) will be administered. Subjects will undergo an endoscopy with biopsy and histology during the screening period. Subjects with CD will be provided access to a study diary to record their daily assessment of well-being, abdominal pain and stool frequency including loose and watery stools. Subjects with UC will be provided access to a study diary to record their daily assessment of their stool frequency and rectal bleeding. The diary must be completed for a minimum of 7 days prior to initiation of open-label treatment as described in [Table 1](#). Finally, adverse events (AEs) will be monitored.

Subjects who are currently taking a biologic treatment or who have received biologic treatment within 12 weeks of the Screening Visit but who are otherwise eligible for study participation based on review of all screening evaluations and results will begin a wash-out period for these medications. Washout is the period between when the subject received their last dose of biologic and when they are eligible to proceed to Visit 2. With the exception of subjects requiring wash-out of the biologic certolizumab pegol (Cimzia), a blood test will be administered to subjects undergoing wash-out 8 weeks after their last dose of biologic treatment to ensure that serum levels of any previous biologic treatments are below the level of detection. If it is confirmed that the levels of previous biologic treatment are undetectable, then the subject will proceed to Visit 2. If the test results indicate that the previous biologic treatment is detectable, the subject will be required to complete a full 12-week wash-out period before proceeding to Visit 2. For subjects receiving the biologic certolizumab pegol (Cimzia) a 12-week wash-out is required.

